14.3.2. Statistical Hypotheses and Level of Significance

The primary efficacy endpoint is the IOP in the study eye measured at the specified time points: 08:00, 10:00 and 16:00 at Week 1, Week 6 and Month 3 visits.

For the primary endpoint, a Mixed Effect Model for Repeated Measurement (MMRM) will be used to test the following hypotheses:

$$H_0: \mu_T - \mu_C > \Delta \text{ versus } H_A: \mu_T - \mu_C \leq \Delta$$

where μ_T and μ_C denote the mean values of the primary endpoint in DE-117/Vehicle arm and Timolol Maleate arm, respectively, and Δ denotes the non-inferiority margin of 1.5 mmHg.

Treatment difference between the DE-117/Vehicle arm and Timolol Maleate arm at each specified time point of each post-baseline visit up to Month 3 will be reported along with 95% confidence intervals. Non-inferiority is established if the upper limit of the two-sided 95% confidence interval for the difference in the mean IOP (0.002% DE-117 - Timolol Maleate) is ≤ 1.5 mmHg at all nine time points and ≤ 1.0 mmHg in majority (5 or more) of the time points. If the upper limit of the 95% confidence interval for the difference is ≤ 0 at all nine time points, superiority of DE-117 to Timolol will be claimed.

If non-inferiority in the primary endpoint is achieved, then the following two key secondary endpoints will be tested sequentially according to hierarchical fixed sequence procedure:

1. Mean diurnal IOP in the study eye at Month 3

The corresponding hypothesis is:

$$H_{0S1}: \mu_{Ts1} - \mu_{Cs1} > \Delta \text{ versus } H_{AS1}: \mu_{Ts1} - \mu_{Cs1} \leq \Delta$$

where μ_{Ts1} and μ_{Cs1} denote the mean diurnal IOP at Month 3 in DE-117/Vehicle arm and Timolol Maleate arm, respectively; and Δ denotes the non-inferiority margin of 1.5 mmHg.

If the hypothesis is rejected at 0.05 significance level, then the following key secondary endpoint will be tested:

2. Mean diurnal IOP in the study eye at Week 1

The corresponding hypothesis is:

$$H_{0S2}: \mu_{Ts2} = \mu_{Cs2} \text{ versus } H_{AS2}: \mu_{Ts2} \neq \mu_{Cs2}$$

Where μ_{Ts2} and μ_{Cs2} denote the mean diurnal IOP at Week 1 in DE-117/Vehicle arm and Timolol Maleate arm, respectively.

14.4. Study Populations

14.4.1. Safety Population

The Safety Population will include all randomized subjects who received at least one dose of the study medication. The safety analysis will be performed on the Safety Population by actual treatment received.

14.4.2. Full Analysis Set

The Full Analysis Set (FAS) will include all randomized subjects who received at least one dose of study medication and provided at least one post-baseline IOP measurement. The efficacy analysis will be performed on the FAS or a subset of the FAS by planned treatment.

14.4.3. Per-Protocol Set

The Per-Protocol Set (PPS) is a subset of the FAS, restricted to the subjects who fulfill the protocol in the terms of the eligibility, interventions, and outcome assessment. It will be the analysis population for some sensitivity analyses. More details will be provided in SAP.

14.5. Handling of Missing Values

The primary analysis of continuous IOP endpoints will be performed using the MMRM analysis on observed cases. As sensitivity analyses, a last-observation-carried-forward (LOCF) approach and a Pattern Mixture Models (PMM) approach may be applied to evaluate the impact of missing data on the primary analysis results. For the binary IOP endpoints, the missing data at Month 3 will be imputed using an LOCF approach.

For medical events including AEs and medical history, completely or partially missing onset and resolution dates will be imputed in a conservative fashion. Same rules will be followed to impute the completely or partially missing start and end dates of non-study medications.

Unless specified otherwise, descriptive summaries will be based on observed cases.

More details on handling of missing data will be provided in the SAP.

14.6. Demographic and Baseline Characteristics

Age, sex, race, ethnicity, iris color, and baseline IOP will be summarized with descriptive statistics by treatment.

Concurrent diseases will be coded using the latest version of Medical Dictionary for Regulatory Activities ([MedDRA](#)). Subjects with any concurrent diseases will be tabulated by primary System Organ Class (SOC) and Preferred Term (PT) specified in the MedDRA.

Subjects using any prior medications that has been used for glaucoma or OHT within 28 days before Screening (Visit 1) will be tabulated by Anatomical Therapeutic Chemical (ATC) levels and PT specified in the latest version of World Health Organization Drug Dictionary Enhanced ([Organization, 2011](#)).

14.7. Efficacy Analyses

Unless specified otherwise, for subjects who discontinue from the study medication per protocol before the Study Exit, the IOP data collected after the study medication discontinuation with any use of non-study IOP lowering medication or surgery will be censored from all efficacy analyses.

14.7.1. Analysis of Primary Efficacy Endpoint

The primary efficacy endpoint is the IOP in the study eye measured at the specified time points: 08:00, 10:00 and 16:00 at Week 1, Week 6 and Month 3 (Visits 3, 4 and 5).

A MMRM will be carried out on observed cases up to Month 3. At each scheduled time point of each visit, least square mean IOP of each treatment arm and 95% confidence interval for the difference in least square means between DE-117/Vehicle and Timolol Maleate will be estimated. Non-inferiority is established if the upper limit of the 95% confidence interval for the difference is ≤ 1.5 mmHg for all nine time points and ≤ 1.0 mmHg for at least 5 out of the 9 time points.

The primary analysis will be based on the FAS. The same analysis will be repeated on the PPS population as a sensitivity analysis. More details on the model specifications will be provided in the SAP.

14.7.2. Analysis of Secondary Efficacy Endpoints

14.7.2.1. Key Secondary Efficacy Endpoints

The key secondary efficacy endpoints are

- Mean diurnal IOP in the study eye at Month 3 (Visit 5), and
- Mean diurnal IOP in the study eye at Week 1 (Visit 3)

A MMRM will be carried out on observed cases up to Month 3. The least square mean diurnal IOP of each treatment arm and 95% confidence interval for the difference in least square means between DE-117/Vehicle and Timolol Maleate at Week 1 and Month 3 will be estimated, respectively. If non-inferiority in the primary endpoint is achieved, then the two key secondary endpoints will be tested sequentially at the 0.05 significance level (2-sided) to control the overall Type I error rate associated with the two comparisons.

The primary analysis will be based on the FAS. The same analysis will be repeated on the PPS population as a sensitivity analysis. More details on the model specifications and multiplicity adjustment will be provided in the SAP.

14.7.2.2. Other Secondary Efficacy Endpoints

Other secondary endpoints to be assessed include:

- Change and percent change from baseline in IOP at each timepoint/post-baseline visit
- Change and percent change from baseline in mean diurnal IOP at each post-baseline visit
- Having a mean diurnal IOP reduction $\geq 20\%$, $\geq 25\%$, or $\geq 30\%$ from Baseline (Visit 2) at each post-baseline visit
- Having a mean diurnal IOP ≤ 18 mmHg at each post-baseline visit

The Continuous secondary endpoints will be analyzed using MMRM on observed cases. More details on the model specifications will be provided in the SAP.

The binary secondary endpoints will be analyzed using the Pearson's chi-square test for a 2×2 contingency table. The Fisher's Exact test may be conducted as a sensitivity analysis.

Subgroup analyses may be performed for secondary endpoints using descriptive statistics.

14.8. Safety Analyses

All safety outcome measures will be summarized descriptively for the Safety Population. The safety outcome measures include AEs, blood pressure and pulse rate, BCVA, slit-lamp biomicroscopy findings, ophthalmoscopy, iris color, eyelash, and eyelid.

AEs will be coded using the latest version of Medical Dictionary for Regulatory Activities (**MedDRA**). Subjects with any AEs will be tabulated by primary SOC and PT specified in the MedDRA. Similarly, subjects with any ocular and non-ocular AEs will be tabulated separately. AEs, ocular and non-ocular will also be summarized by relationship to treatment and maximum severity. In addition, SAEs and discontinuations due to AEs will be summarized.

Safety parameters listed in [Section 12.2.1](#) and [Section 12.2.2](#) will be summarized using descriptive statistics by actual treatment received. Changes from baseline in these safety parameters will also be summarized by treatment.

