12.2.1. Ocular Assessments

Ocular assessments include:

- BCVA
- Slit-lamp biomicroscopy findings: anterior chamber cells, anterior chamber flare, lid hyperemia, lid edema, conjunctival hyperemia, conjunctival chemosis, corneal edema, corneal staining, keratic precipitate, lens, anterior synechiae of iris and posterior synechiae of iris
- Ophthalmoscopy variables: glaucomatous optic nerve
- Iris color/eyelash/eyelid

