## 4.4. Safety-Related Definitions

### 4.4.1. Adverse Event

Under Protocol 011709IN, an AE is defined as any untoward medical occurrence that occurs in a study subject, regardless of the causal relationship with the study treatment. An *on-study* AE can occur any time after the date of informed consent through the last study visit. An AE will be considered as *treatment-emergent* if the onset date of the AE occurred on or after the treatment start date till up to 2 days (twice the scheduled dosing interval) after treatment end date.

Treatment-emergent AEs (TEAEs) are a subset of on-study AEs. Both on-study and TEAEs will be collected, but only TEAEs will be tabulated.

The severity of each AE will be graded by the Clinical Investigator as Mild, Moderate, or Severe. AEs will also be rated by the Investigator as to their causality/relationship to the study drug.

Each AE will be classified into a system organ class (SOC) and coded to a preferred term (PT) using Medical Dictionary for Regulatory Activities (MedDRA), Version 21.1 published in 2018.

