#### 4.4.1.3. Suspected Adverse Reaction

An AE will be counted as a *suspected adverse reaction* (SAR) if the Clinical Investigator answered ‘Related’ to the AE eCRF question “Relationship to Study Drug”.

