### 9.1. Adverse Events

AEs, SAEs, SARs, serious SARs, and significant AEs (AEs leading to study drug discontinuation and AEs leading to death) will be tabulated by type of AEs by treatment arm using actual treatment received for all AEs, ocular AEs, and non-ocular AEs separately.

Besides the overall AE summary, AEs, SAEs, SARs, serious SARs will be tabulated by SOC and preferred term for all AEs, ocular AEs, and non-ocular AEs separately. A subject who experienced multiple AEs within a SOC or preferred term will be counted only once for that SOC or preferred term. Non-serious AEs (including number of events) and ESIs will also be summarized by SOC and preferred term.

All the AE summaries will be performed for double-masked, open-label, and entire study periods separately. For double-masked period summaries, overall AE summary, summary of AE by SOC and PT, SAEs, SARs, and serious SARs will also be tabulated on pediatric subjects separately. For open-label and entire study period summaries, tabulations by treatment received during double-masked period will be provided as well as overall summary for subjects exposed to DE-117. So, for subjects who exposed to the Timolol arm during the double-masked period, their AE summaries under the Overall DE-117 column will be those AEs that started during the open-label treatment period.

AEs, SAEs, SARs, serious SARs, ocular AEs, AEs leading to death, AEs leading to study drug discontinuation, non-TEAEs, and ESIs, if any, will be listed separately.

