## **9.3. Slit-lamp Biomicroscopy**

For each biomicroscopy parameter, frequency and percentage of rating scores will be summarized by treatment, analysis visit and study period (double masked and open-label) for study eyes and fellow eyes, separately. In addition, any clinically significant worsening (increase) from baseline will be summarized and listed.

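### The SAP has no table of adverse events by maximum severity, which Protocol 14.8 requires, and gives no grade criterion for slit-lamp worsening

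*Protocol*

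**What the plan says.** Protocol 14.8 makes two commitments that matter here. On adverse events: "AEs, ocular and non-ocular will also be summarized by relationship to treatment and maximum severity". On the parameters in 12.2.1 and 12.2.2: "Changes from baseline in these safety parameters will also be summarized by treatment". Section 12.2.1 includes the slit-lamp examination ("Slit-lamp biomicroscopy findings: anterior chamber cells, anterior chamber flare, lid hyperemia, lid edema", and further findings).

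On adverse events, SAP 4.4.1 keeps the grading: "The severity of each AE will be graded by the Clinical Investigator as Mild, Moderate, or Severe". SAP 9.1 then sets out the tables: "AEs, SAEs, SARs, serious SARs will be tabulated by SOC and preferred term for all AEs, ocular AEs, and non-ocular AEs separately". It adds an overall summary, discontinuations and deaths due to AEs, non-serious AEs, events of special interest, and separate pediatric tables. None of these is broken down by severity. Relationship is kept, because SAP 4.4.1.3 defines a suspected adverse reaction as an event that the investigator marked as related.

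On the slit lamp, SAP 9.3 says that for each parameter "frequency and percentage of rating scores will be summarized by treatment, analysis visit and study period (double masked and open-label"), for study and fellow eyes separately. It then says: "In addition, any clinically significant worsening (increase) from baseline will be summarized and listed".

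SAP 10 lists the changes to the protocol's analyses. There are three: the FAS definition, an added key secondary endpoint, and removal of LOCF.

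**The concern.** The safety objective is comparative: DE-117 against Timolol. SAP 1 makes the SAP's analyses the basis of the study report, so a table that the SAP omits will by default be missing from the report, even though Protocol 12.1.1.2 has maximum severity recorded for every event.

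Two comparisons are at stake. The first is AE severity. Protocol 12.1.1.1 keeps severity distinct from seriousness, so an event can be severe without being serious. If it also does not stop treatment, no planned table would mark it as severe.

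The second is worsening within an eye on slit-lamp examination. The ocular inflammation summary in SAP 9.1.1 is built from reported AE preferred terms. Slit-lamp grading is the planned examination-based check on hyperemia and on anterior chamber cells and flare. Its by-visit grade distribution does not say how many eyes got worse, and the summary that would say so has no stated criterion.

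**Working it through.** The plan states no figure on this point, so the check is a comparison of text with two small illustrations.

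**Step 1: protocol commitments against SAP provisions.**

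| Protocol 14.8 | SAP provision | Declared in SAP 10? |
|---|---|---|
| AEs by relationship | SAR and serious SAR tables (9.1) | Not needed; carried over |
| AEs by maximum severity | None; severity is only defined (4.4.1) | No |
| Slit-lamp change from baseline, by treatment | Summary of clinically significant worsening, no grade rule (9.3) | No |

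**Step 2: how the SAP treats comparable measures.**

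- BCVA (9.2): change of at least 0.2 logMAR.
- Cup-to-disc ratio (9.4): increase of at least 0.2.
- Optic nerve findings (9.4): worsening of at least 2 units.
- Retina/macula/choroid and vitreous (9.4): shift from baseline at Month 3.
- Slit lamp (9.3): no threshold and no shift table. Table 6 of the SAP supplies none either.

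A single rule is not self-evident. Under Protocol 21.3.7, cells are graded 0, 0.5, 1, 2, 3, 4, flare 0 to 4, and the remaining parameters 0 to 3. A move in cells from 0 to 0.5 is an increase, but only half a unit.

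**Step 3: what a by-visit grade table can show.** Suppose an arm has n0 eyes at grade 0 and n1 eyes at grade 1, with the same counts at Baseline and Month 3. The number of eyes that went from 0 to 1 can be anything from 0 to min(n0, n1), because each new finding can be offset by one that resolved. The counts below are assumed; only the 200 per arm comes from the sample size section.

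- n0 = 180, n1 = 20: 0 to min(180, 20) = 20 eyes, or 0% to 20/200 = 10%.
- n0 = 160, n1 = 40: 0 to min(160, 40) = 40 eyes, or 0% to 40/200 = 20%.

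The printed table is the same across each range.

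**Step 4: AE severity, again with assumed counts.** Take 200 per arm and an event in 40 subjects in each arm (40/200 = 20%). Let it be severe in 10 subjects in one arm (10/200 = 5%) and in 1 in the other (1/200 = 0.5%). If no event is serious or leads to discontinuation, and the same number in each arm are rated related, the planned tables show 20% against 20% and equal SAR counts. A maximum-severity table would show 5% against 0.5%. No p-value is attached, because SAP 6 plans no testing of safety measures.

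**The case against.** The strongest reply is that the planned tables already catch much of what severity would show. SAP 9.1 compares serious events, related events, deaths and discontinuations by arm. SAP 9.1.1 adds inflammation that needed steroids or NSAIDs, which overlaps with the protocol's definition of a severe event as one needing medical intervention. This stands. A reader might infer that two arms with different severity would give identical tables throughout; that is so only under the conditions in Step 4. The gap is confined to severe events that are non-serious and do not stop treatment.

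A reader might also infer that the sponsor chose to withhold severity. The documents do not support that. Protocol 14.8 is not revoked, SAP 4.4.1 still defines the grades, and AEs are to be listed. It is an undeclared omission.

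On the slit lamp, SAP 9.3 does plan a worsening summary, and Protocol 14.8 prescribes neither a shift table nor a threshold. With randomized arms, grade distributions at a visit are a fair comparison of net effect. Offsetting also needs affected eyes at baseline. A history of iritis or uveitis is excluded, so cells and flare should be near zero at entry, and new inflammation would appear in the by-visit table. The limitation therefore bears more on findings such as mild hyperemia.

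Finally, a reader might infer that the analyst would set the worsening rule after seeing the data. The SAP does not say who judges clinical significance. It may be the investigator, who is masked through Month 3. Equally, nothing fixes a rule before the unmasked Month 3 analysis in Protocol 14.2, so the question is open.

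**Conclusion.** The point holds in a limited form. The maximum-severity AE summary required by the protocol is absent from SAP 9.1 and undeclared in SAP 10. The slit-lamp change-from-baseline commitment is met only by a summary without a grade criterion, unlike the SAP's treatment of BCVA, cup-to-disc ratio and optic nerve findings.

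The size is modest: descriptive safety tables only, on data already collected, with no effect on efficacy inference. The percentages in Steps 3 and 4 show what the tables could miss under assumed counts; they are not predictions. The conclusion rests on the SAP text as supplied. The appendix contents are not shown, but SAP 8.1.1.2 describes Appendices A and B as code for the MMRM and the pattern-mixture model, so they are unlikely to contain these definitions. The change should be made because it restores a protocol commitment at small cost.

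**What to change.** **SAP 9.1.** Add treatment-emergent AEs by SOC, preferred term and maximum severity, for all, ocular and non-ocular events, by arm and by period. Count each subject once, at the worst severity.

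**SAP 9.3.** Keep the existing summary and do one of the following:

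- add a shift table of baseline grade against worst post-baseline grade for each of the 12 parameters, by arm, period, and study or fellow eye; or
- fix, before unmasking, a grade-increase rule that works for the 0 to 3 scales, for flare (0 to 4), and for the 0/0.5/1 to 4 cell scale, and state who applies it.

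If either protocol commitment is not to be met in full, SAP 10 should say so and give the reason.

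**Cost.** Shells and programming, with no new data. The AE addition is about 3 event sets × 3 periods = 9 tables. Full shift tables come to 12 parameters × 2 eyes × 2 periods = 48 panels. The grade-increase rule is the cheaper choice if that is too many.

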15. DIRECT ACCESS TO SOURCE DATA/DOCUMENTS

The Principal Investigator will allow representatives of Santen's monitoring team (or designee), the governing IRB or IEC and other applicable regulatory agencies to inspect all study records, eCRFs, recruitment materials and corresponding portions of the subject's medical records at regular intervals throughout the study. These inspections are for the purpose of verifying adherence to the protocol, completeness, and exactness of the data being entered onto the eCRF, and compliance with the ICH-GCP or other regulatory agency regulations.

15.1. Study Monitoring

Before an investigational site can enter a subject into the study, a representative of Santen (or designee) will evaluate the investigational study site to:

- Determine the adequacy of the study facilities.
- Review with the Principal Investigator and his/her designee their responsibilities with regard to protocol procedures adherence, and the responsibilities of Santen (or designee).

During the study, Santen (or designee) will have regular contact with the investigational site, for the following:

- Provide information and support to the Investigator(s).
- Confirm that facilities remain acceptable.
- Assess adherence to the protocol and ICH-GCP.
- Perform investigational product accountability checks and quality control procedures.
- Ensure the on-going implementation of accurate data entry in the eCRF.
- Perform source data verification, including a comparison of the data in the eCRFs with the subject's medical records and other records relevant to the study. This will require direct access to all original records for each subject (e.g., clinic charts).
- Record and report any protocol deviations not previously sent to Santen.
- Confirm AEs and SAEs have been properly documented on eCRFs and confirm any SAEs have been forwarded to Santen and those SAEs that met criteria for reporting have been forwarded to the IRB or IEC.
- Confirm sites have a complete record of all study IND Safety Reports and filed them with the IRB or IEC.

Santen (or designee) may remotely access the eCRFs at any time during the study for centralized monitoring. Santen (or designee) will be available between visits if authorized study staff need study related information or support.

15.2. Audits and Inspections

The Principal Investigator will allow Santen (or designee), the governing IRB or IEC, and applicable regulatory agencies to audit and inspect any aspect of the study, including all study records, eCRFs, recruitment materials, and corresponding portions of the subject's charts and medical records at any time during the study. These study records must be retained at the study site and made available for audits and inspections. The purpose of these audits and inspections is to verify adherence to the protocol, completeness and accuracy of the eCRF data, and compliance with ICH-GCP guidelines and applicable regulatory requirements.

The Principal Investigator (or his/her designee) will notify Santen (or designee) should the site be audited or inspected by the governing IRB or IEC, and applicable regulatory agencies. Santen (or designee) will also notify the investigational site of any known pending site audits or inspections planned by Santen (or designee), governing IRB or IEC and regulatory agencies.

